- 3. Primary outcome: Significance will be determined with a mixed model for repeated measures. MADRS scores obtained on postoperative Day 1, 2, and 3 will be combined and treated as a single timepoint in a mixed model, rather than separately testing each day for significance which can inflate type I error rate. We will use an uncorrected two-sided alpha of 0.05 as a cutoff for statistical significance.
- 4. Secondary outcomes will be compared using t-tests for continuous and ordinal variables and chi-squared tests for categorical variables. No correction for multiple comparisons needed due to the exploratory nature of these outcomes.

D. Study Procedures from Screening to Closeout

Screening

Patients may be informed about the study if they are contacted as part of a perioperative mental health screening service (IRB-54043, approved as not clinical research and not requiring IRB oversight), at which time they may be offered psychiatric care referrals, counseling and information about multiple ongoing clinical trials. Potential subjects may also be introduced to the study through handouts and brochures placed in surgical and pre-anesthesia clinics. Patient identified through Epic as likely to be depressed may also be approached at pre-op appointments and study staff will describe the study and consent if appropriate. Surgery schedulers will ask surgery patients if they are interested in the study and give them a letter or by reading/sending a phone script. Specific procedures for introducing patients to the study and which patient data will be assessed to identify depression are described in detail in section 8g.

Informed consent will be obtained prior to full evaluation of inclusion and exclusion criteria.

Informed consent may be obtained in one of two ways: in-person or over the phone.

In-person consent:

If the patient has an already scheduled preoperative appointment at Stanford, research staff may meet the patient before or after this appointment to obtain informed consent. Alternatively, the patient may choose to make a separate visit to Stanford Medical Center for the consenting process.

Phone consent:

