The first 5 patients that meet inclusion/exclusion criteria will be entered into the open-label feasibility study; all will receive a ketamine infusion. All other patients enrolled thereafter will be entered into the double-blind, randomized, placebo-controlled study. The day of surgery will be considered Day 0 of the study. Baseline assessments must be performed before the patient receives any psychoactive premedication (e.g. midazolam, fentanyl, gabapentin, oxycodone). Assessments will be performed either in the hospital or, if the patient has been discharged (typically on postoperative Day 2), by phone.

Participants who remain in the hospital for at least 24 hours post-surgery will be asked to give blood samples for immunological analyses. Two blood samples (10mL for each draw) will be collected from each participant.

Day 0 (Baseline Assessments):

By Physician or Study Staff:

- Vital Signs
- Concomitant Medication Review
- Adverse Events Review
- Montgomery-Asberg Depression Rating Scale (MADRS)
- Collect breath sample #1

By the Participant, reviewed by Investigators:

- Hospital Anxiety and Depression Scale (HADS)
- Brief Pain Inventory (BPI)

Day 0 (During Surgery):

By the Intraoperative Anesthesiologist:

- Ketamine infusion or placebo (saline) infusion
- Continuous physiological monitoring
- SedLine® Brain Function Monitor to evaluate depth of anesthesia/sedation
- Collect breath sample #2, after infusion is complete

Day 1:

By Physician or Study Staff:

- Vital Signs
- Concomitant Medication Review
- Adverse Events Review
- Montgomery-Asberg Depression Rating Scale (MADRS)

By the Participant, reviewed by Investigators:

- Hospital Anxiety and Depression Scale (HADS)
- Brief Pain Inventory (BPI)

Day 2:

By Physician or Study Staff:

- Vital Signs (inpatient only)
- Concomitant Medication Review
- Adverse Events Review
- Montgomery-Asberg Depression Rating Scale (MADRS)

By the Participant, reviewed by Investigators:

- Hospital Anxiety and Depression Scale (HADS)
- Brief Pain Inventory (BPI)

Day 3 (inpatient or via phone):

By Physician or Study Staff:

- Vital Signs (inpatient only)
- Concomitant Medication Review
- Adverse Events Review
- Montgomery-Asberg Depression Rating Scale (MADRS)

By the Participant, reviewed by Investigators:

- Hospital Anxiety and Depression Scale (HADS)
- Brief Pain Inventory (BPI)

Day 5 (inpatient or via phone):

By Physician or Study Staff:

- Vital Signs (inpatient only)
- Concomitant Medication Review

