STATISTICAL ANALYSIS PLAN

Official Title:

Intraoperative Ketamine Versus Saline in Depressed Patients
Undergoing Anesthesia for Non-cardiac Surgery

NCT Number: 03861988

Protocol last edited: 10/28/2021

Statistical Analysis Plan (SAP)

Section 1: Administrative Information

1. Title and trial registration

1a. Title

Intraoperative Ketamine Versus Saline in Depressed Patients Undergoing Anesthesia for Non-Cardiac Surgery

1b. Trial registration number

ClinicalTrials.gov Identifier NCT# 03861988

2. SAP version: 2.0

3. Protocol version: Stanford eProtocol ID 49114, last revision submitted 8/9/21

4. SAP revisions

4a. SAP revision history

10/21/2019 – version 1.0 (originally included in the study protocol)

10/28/2021 – version 2.0 (created a new, separate SAP document)

4b. Justification for each SAP revision

Version 1.0 to 2.0:

- 1) In our original protocol, recruitment was limited to patients with symptomatic depression presenting for hip and knee arthroplasty at Stanford. Patients undergoing this type of surgery have a predictable postoperative course, which guided our primary endpoint selection. We encountered significant difficulties recruiting patients during the COVID-19 pandemic. Therefore, we expanded eligibility criteria by including patients presenting for a wider variety of surgical procedures, which are described in our updated protocol. To account for the likely increased variability of postoperative recovery in this broader population, we updated our primary endpoint to include data from the first 3 days after surgery, instead of only a single day after surgery.
- 2) In our original protocol, the primary outcome measure was defined as the sum of scores from a clinician-administered scale and a self-report scale. During the recruitment phase of our trial, and prior to unblinding, we presented our analysis plan to a panel of statisticians in the Department of Biomedical Data Sciences at Stanford University. The panel recommended that we could improve the interpretability and reduce the variance in our primary outcome by only using one validated measure (rather than a composite score) as our primary outcome measure. Based on this recommendation, we updated our primary outcome measure to only include the clinician-administered scale (the Montgomery-Asberg Depression Rating Scale).

4c. Timing of SAP revisions

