Non-emergent deviations are defined as those that do not occur in an emergency situation. Examples potentially encountered in our study include, but are not limited to: 1) participant is randomized to a treatment intervention but does not meet eligibility criteria, 2) the anesthesiologist administered the study drug incorrectly or incompletely, 3) the participant inadvertently received the intervention meant for the other trial arm, 4) the participant was not available for assessment of the planned outcome either because of loss to follow-up or for another reason, 5) study staff were not available for assessment of the planned outcome either because of a personal emergency or another reason.

19d. Which protocol deviations will be summarized

All emergency and non-emergent protocol deviations will be summarized.

20. Analysis populations

As recommended by CONSORT guidelines for parallel group randomized controlled trials, intention-to-treat and per-protocol analyses (if needed) will be performed and reported for all planned outcomes to allow readers to interpret the effects of the intervention.

Section 5: Trial Population

21. Screening data

Screening data to be collected and reported in CONSORT flow diagram include:

Patient Health Questionnaire score

HADS-MADRS composite score

English-speaking status

Age

Body mass index

History of significant CNS disease or brain surgery

History of moderate to severe substance use disorder (except nicotine)

History of schizophrenia, schizoaffective disorder, or psychosis

Chronic high dose opioid use (>90 morphine milligram equivalents per day)

High suicide risk

Other reasons

22. Eligibility

22a. Inclusion criteria

A subject will be eligible for inclusion only if all of the following criteria are met:

1. Male or female, 18 to 80 years of age, inclusive, at screen.
2. Able to read, understand, and provide written, dated informed consent prior to screening. Participants will be deemed likely to comply with study protocol and communicate with study personnel about adverse events and other clinically important information.
3. PHQ-8 score ≥ 12 .

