A mixed model for repeated measures (MMRM) will be used to analyze the difference in postoperative MADRS score which is our primary outcome. The model will include treatment and time as fixed effects, with a treatment*time interaction term. The data will be modeled with random intercepts and random slopes to account for variation in baseline scores and postoperative trajectories. MADRS scores measured on postoperative Day 1, 2, and 3 will be combined and treated as a single timepoint in the mixed model, rather than separately testing each day for significance which can inflate type I error rate. Postoperative Days 1, 2, and 3 were chosen due to previously published data showing that the antidepressant effect of ketamine persists up to 3 days after administration.

27b. Sensitivity analyses

Sensitivity analyses will be conducted for the following scenarios:

- 1) Missing data: See section 28
- 2) Intention-to-treat vs per-protocol analysis (if needed)
- 3) MMRM analysis using HADS (self-report) as a confirmatory measure
- 4) MMRM analysis using the previously proposed primary outcome measure (a composite score defined as the sum of scores from MADRS and HADS)

27c. Subgroup analyses

We will conduct several pre-specified subgroup analyses. While the trial will not specifically be powered for these subgroups, we hope to gain further insight into sub-populations that may particularly benefit from the intervention. Example subgroup analyses to be considered:

- 1) Preoperative use of antidepressants
- 2) Preoperative use of opioids
- 3) Intraoperative exposure to nitrous oxide
- 4) Intraoperative exposure to opioid infusions
- 5) Postoperative use of neuraxial or peripheral nerve catheters

28. Missing data

For the primary outcome, it will be assumed that the missing data are missing at random. Sensitivity analysis will be performed to evaluate the robustness of the MMRM to the missing-at-random assumption.

29. Adverse events

Adverse events will be recorded in the Stanford REDCap database using the Adverse Event (AE) Form and Serious Adverse Event (SAE) Form. Refer to document GUI-P13 (<https://researchcompliance.stanford.edu/panels/hs/policies/guidances>) for definitions of AEs and SAEs. All AEs and SAEs will be summarized.

30. Statistical software

Statistical analyses will be conducted using R statistical software. Data figures for visualization will be generated using either R or Graphpad Prism.

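### Merging Days 1 to 3 into one timepoint, with no day term and no rule for a missing day, leaves the primary estimate open to a small shift if missed days differ by arm

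*SAP*

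**What the plan says.** SAP 27a sets the rule: "MADRS scores measured on postoperative Day 1, 2, and 3 will be combined and treated as a single timepoint in the mixed model". SAP 17 repeats it, and Protocol 8C, Analysis Plan item 3, has it too: "MADRS scores obtained on postoperative Day 1, 2, and 3 will be combined and treated as a single timepoint in a mixed model". The reason given is to avoid testing each day separately.

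On the model, SAP 27a says: "The model will include treatment and time as fixed effects, with a treatment*time interaction term". It adds: "The data will be modeled with random intercepts and random slopes to account for variation in baseline scores and postoperative trajectories". Since the three days are one level of time, no fixed effect separates them.

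On missing data, SAP 28 says: "For the primary outcome, it will be assumed that the missing data are missing at random". It promises a sensitivity analysis to that assumption but names no method. Missed assessments are foreseen. SAP 19c lists as a possible deviation that "the participant was not available for assessment of the planned outcome either because of loss to follow-up or for another reason". Assessment mode can also change inside the window. Protocol 8D has patients assessed in hospital or, "if the patient has been discharged (typically on postoperative Day 2), by phone".

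The documents do not say whether combining means stacking the available rows, averaging the available days or using complete windows only. They give no rule for a participant seen on one or two of the three days.

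**The concern.** A likelihood-based mixed model makes use of missing-at-random data through the terms it contains. If day is a term, a participant seen only on Day 1 informs the Day 1 mean, and the later means are estimated with allowance for that participant's Day 1 score. If day is removed, the same Day 1 score is taken as an observation of the whole window. Should scores be falling, it is systematically too high for that purpose. A participant who misses only Day 1 errs the other way.

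The random slopes do not cure this. They describe how individuals depart from the mean path, and the mean path has no day inside the window.

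The primary estimate is at stake. If one arm has more missing late days than the other, the comparison weights the days differently in the two arms, and part of the ordinary postoperative time trend enters the treatment difference.

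**Working it through.** **Inputs from the documents.** SAP 11: mean decreases of 10.9 (SD 8.9) and 2.8 (SD 3.6), so a planning difference of 10.9 − 2.8 = 8.1; 38 participants before attrition; 2 of 40 (5%) added for attrition. Protocol 8C, Sample Size: 5 of 20 per group (25%) for dropout. Neither document gives a slope over Days 1 to 3 or a rate of missed days by arm; those below are assumptions.

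**The plan's own figure.** With SD 8.9 in both arms, n per arm = 2 × (1.960 + 0.842)² × 8.9² / 8.1² = 18.95, so 19 per arm and 38 in total, as stated. At 20 per arm, power is 82.1%.

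**Size of the shift when available days are averaged.** Let scores change by s points per day in both arms, and let a fraction f more of one arm lack some days. The full window has mean day 2.

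- Day 3 missing: mean observed day 1.5, shift 0.5 × s × f.
- Days 2 and 3 missing: mean observed day 1, shift 1 × s × f.
- Day 1 missing: mean observed day 2.5, shift 0.5 × s × f in the opposite direction.

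| Excess loss f | s = 1 | s = 2 | s = 4 |
|---|---|---|---|
| 5% | 0.03 to 0.05 | 0.05 to 0.10 | 0.10 to 0.20 |
| 25% | 0.13 to 0.25 | 0.25 to 0.50 | 0.50 to 1.00 |

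Each cell runs from Day 3 missing to Days 2 and 3 missing. As a share of 8.1 points, the table spans 0.025 / 8.1 = 0.3% to 1.00 / 8.1 = 12%.

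**The same question in a mixed model with stacked rows.** Simulation: 20 per arm, baseline plus Days 1 to 3, random-intercept SD 6.5, residual SD 6.0, 600 runs. The merged estimate was compared with the equal-weight average of day-specific effects, with these differences in absolute value:

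- complete windows: 0.00, with empirical SE 2.28 for both;
- 25% missing Days 2 and 3 in both arms, equal slopes: 0.03;
- 25% missing Days 2 and 3 in one arm only: 0.32 at s = 2 and 0.67 at s = 4;
- 25% missing in both arms, slopes differing by 2 points per day: 0.31. Here the arms share the same mix of days, but the estimate moves towards the Day 1 effect.

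With 25% missing in one arm at s = 2, the empirical SE was 2.27 day-specific and 2.25 merged.

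**Whether missed days can differ by arm in a blinded trial.** Give both arms one rule under which the chance of missing Days 2 and 3 depends only on the Day 1 score (assumed log-odds 0.15 per point, 25% missing on average). This is missing at random. With a true difference of 8.1 and the same SDs, saline loses about 34% and ketamine about 16%, because treatment lowers Day 1 scores. The merged stacked estimate is about 8.4 when scores fall 2 points per day and 8.6 to 8.7 at 4 points per day. The day-specific average gives 8.1 in both (Monte Carlo error 0.05 to 0.08). In this scenario the bias favours ketamine.

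**Consequence for the test.** A shift towards the null of 0.5 or 1.0 points takes power from 82.1% to 77.0% or 71.3%. Under no effect, with 25% of one arm and 5% of the other lost after Day 1, a simulation of per-patient means (20 per arm, SD 8, adjacent-day correlation 0.8, 4,000 runs) gave false differences of 0.43 and 0.79 at 2 and 4 points per day. The formula gives (0.25 − 0.05) × 2 = 0.4 and (0.25 − 0.05) × 4 = 0.8. Rejection stayed near 5% to 6%.

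**The case against.** The strongest reply is that nothing in the documents says missed days will differ by arm. Allocation is 1:1, participants, care providers and assessors are masked, and assessment continues by phone or video after discharge. The two attrition allowances are whole-study figures and neither is split by arm; 25% in one arm against 5% in the other is a stress test, not a documented imbalance. The slopes have no anchor either: 4 points per day means an 8-point fall from Day 1 to Day 3, about the whole planning effect. At 5% excess loss the shift is at most 0.2 points, against a simulated SE of about 2.3. All of this stands, so the point must be conditional. It does not remove the point, because blinding does not prevent imbalance when missingness follows earlier scores and treatment changes those scores.

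A reader might infer several stronger things that the documents do not support.

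- That the plan amounts to last observation carried forward. The combining rule is unstated, and in a stacked model a participant with one row carries less weight than one with three.
- That missing-at-random is false here. Merging days leaves the missingness mechanism untouched; the fault is a term omitted from the mean model.
- That SAP 27a expects the effect to fade inside the window. It says the effect lasts as long as three days, as a reason to include all three.
- That SAP 4b predicts a daily trend. Its phrase, "To account for the likely increased variability of postoperative recovery in this broader population", concerns spread between patients and explains why three days were preferred to one.

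The promised sensitivity analysis and the recording of withdrawal timing and reasons (SAP 24) help a little. With no method named, they cannot be relied on to detect a shift from the mix of days.

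**Conclusion.** The point holds in conditional form. The plan collapses three days into one level, drops day from the mean model and gives no rule for an incomplete window. The estimate shifts if scores trend within the window and missed days differ by arm. It can also move, by reweighting the days, when missingness is balanced but the slopes differ. One cannot conclude that the primary contrast does compare different mixes of days: with complete windows the merged and day-specific analyses are identical, and with balanced missingness and equal slopes they nearly are.

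The likely size is small. Under assumed slopes of 1 to 4 points per day it is at most about 0.2 points at 5% excess loss in one arm, and about 0.1 to 1.0 points at 25%, against 8.1 points. The main issue is bias in the estimate, with some loss of power if the shift is towards the null and little effect on type I error. The change is worth making because it is cheap and the stated reason for merging, having one test, is met equally well without merging.

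**What to change.** In SAP 17 and 27a and Protocol 8C item 3, keep Days 1, 2 and 3 as separate levels of categorical time with treatment-by-day terms. Prespecify the within-patient covariance (for example, unstructured) and name one simpler structure to use if the model does not converge. Make the primary test the single equal-weight average of the three day-specific treatment differences, at two-sided 0.05, reported with its 95% confidence interval. State that a participant with one or two of the three days enters with the days observed. In SAP 28, name the method for the missing-at-random sensitivity analysis.

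This remains one test, so the multiplicity argument in SAP 17 is preserved; three separate tests would give 1 − 0.95³ = 14.3% if independent. Alpha, sample size and the Day 1 to 3 target do not change, and no new data are needed. The downside is a few more parameters with 40 participants, which is why the fallback covariance must be named. Because SAP 4c records that the primary outcome was already revised during enrolment, this change should be dated, justified in the revision history and made before unblinding.

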- 2) MME/day, if on opioids (mean, SD)
- 3) Anticonvulsants (n, %)
- 4) Benzodiazepines (n, %)
- 5) Muscle relaxants (n, %)
- 6) Antidepressants (n, %)
- 7) Antipsychotics (n, %)
- 8) Lithium (n, %)
- 9) Prescription sleep medications (n, %)
- 10) Opioid antagonists (n, %)
- 11) Stimulants (n, %)

25c. Surgical characteristics

- 1) Type of surgery
 - a. ENT/OMF (n, %)
 - b. Thoracic (n, %)
 - c. Breast (n, %)
 - d. Plastic non-breast (n, %)
 - e. Spine (n, %)
 - f. Major joint (n, %)
 - g. Other orthopedic/limb (n, %)
 - h. Intraabdominal general surgery (n, %)
 - i. Urologic and gynecologic (n, %)
 - j. Vascular (n, %)
 - k. Transplant (n, %)
- 2) Type of anesthesia
 - a. General anesthesia (n, %)
 - b. Monitored anesthesia care (n, %)
- 3) Intraoperative nitrous oxide (n, %)
- 4) Intraoperative propofol infusion (n, %)
- 5) Intraoperative opioid infusion (n, %)
- 6) Length of surgery (hours, mean and SD)
- 7) Peripheral or neuraxial catheter placed (n, %)

Section 6: Analysis

26. Outcome definitions

26a. Primary outcome

Postoperative MADRS scores from postoperative Days 1 through 3.

26b. Main secondary outcomes

- 1) Proportion of participants with clinical response (defined as a $\geq 50\%$ reduction in MADRS score from baseline).
- 2) Proportion of participants with remission (defined as a MADRS score of ≤ 12 on day 14).

26c. Other exploratory secondary outcomes

- 1) MADRS scores at postoperative Days 5, 7, and 14
- 2) Hospital Anxiety and Depression Scale
- 3) Cumulative inpatient opioid use
- 4) Hospital length of stay
- 5) Average inpatient opioid use per day
- 6) Opioid use at postop day 7
- 7) Opioid use at postop day 14
- 8) Postoperative numeric pain scores
- 9) Postoperative pain interference scores

27. Analysis methods

27a. Analysis of the primary outcome

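### Three of the five example subgroups in SAP 27c are defined by exposures observed after randomization that ketamine could influence, so effects within them may be biased

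*SAP*

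**What the plan says.** SAP 27c opens with "We will conduct several pre-specified subgroup analyses". It adds that the trial is not powered for them, states the hope of finding sub-populations that benefit in particular, and presents the list as examples to be considered. The five items are:

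1. antidepressants taken before surgery
2. opioids taken before surgery
3. nitrous oxide given during surgery
4. opioid infusions during surgery, worded as "Intraoperative exposure to opioid infusions"
5. catheters after surgery, worded as "Postoperative use of neuraxial or peripheral nerve catheters"

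SAP 25c tabulates intraoperative nitrous oxide, intraoperative opioid infusion and catheter placement as surgical characteristics, under the general heading of baseline patient characteristics. It gives no time at which any of them starts.

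SAP section 10 randomizes participants as they enter the study, and the Study Procedures Matrix in the protocol puts randomization in the screening column. The study infusion begins after induction (protocol, Infusions; SAP section 9). Care providers are masked (SAP section 9). SAP 26c includes "Cumulative inpatient opioid use" among the exploratory outcomes.

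**The concern.** A subgroup effect is a randomized comparison only if membership cannot depend on treatment. Items 1 and 2 meet that condition. Items 3 to 5 need not. If ketamine changes who gets an opioid infusion, the ketamine patients who still get one differ in kind from the saline patients who get one, and the arms within that subgroup are no longer comparable.

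The documents make such an influence plausible. Ketamine is given to supplement anesthesia (protocol section 5A), and opioid use and pain are trial outcomes. The anesthesiologist has continuous physiological monitoring and a depth-of-anesthesia monitor, so can respond to the drug's effects while unaware of the arm.

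What is at stake is interpretation. Section 27c wants these splits to show who benefits. The objectives in SAP section 8 also raise the possibility that other anesthetics block ketamine's effect, and a nitrous oxide or opioid-infusion subgroup would readily be cited for that. Saying that the subgroups are not powered warns the reader of imprecision, not of lost comparability.

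**Working it through.** **Timing of each item**

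| 27c item | Relative to randomization | Relative to the study infusion |
|---|---|---|
| 1. Preoperative antidepressants | Not set by treatment | Before |
| 2. Preoperative opioids | Not set by treatment | Before |
| 3. Intraoperative nitrous oxide | After | Not stated |
| 4. Intraoperative opioid infusion | After | Not stated |
| 5. Postoperative catheter use | After | After as worded; placement may be earlier |

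Three of the five are therefore observed after randomization, and 27c has no rule tying them to status before the infusion.

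**Planning scale.** SAP section 11 gives mean decreases of 10.9 (SD 8.9) and 2.8 (SD 3.6), a difference of 10.9 − 2.8 = 8.1. With SD 8.9 in both arms, n per arm = 2 × (1.960 + 0.842)² × 8.9² / 8.1² = 18.95. This rounds up to 19, or 38 in total, which is the SAP's figure. The values 8.1 and 8.9 are used below.

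**Possible size of the bias, opioid infusions only.** None of the following inputs is in the documents:
- U is a standard normal latent severity, worth b = 3 or 5 MADRS points per SD.
- Opioid need is standard normal and correlates 0.7 with U. An infusion is given when need exceeds 0, so 50% of saline patients get one.
- Ketamine lowers need by c SD, so a ketamine patient gets an infusion only when underlying need exceeds c.

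With φ and Φ the normal density and distribution function, and φ(0)/0.5 = 0.798:
- Bias with infusion = 0.7b × [φ(c)/(1 − Φ(c)) − 0.798]
- Bias without infusion = 0.7b × [0.798 − φ(c)/Φ(c)]

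Worked case, c = 0.5 and b = 5. Ketamine-arm use is 1 − Φ(0.5) = 31%. With infusion: 3.5 × (1.141 − 0.798) = 1.20. Without: 3.5 × (0.798 − 0.509) = 1.01. Bias in the contrast: 1.20 − 1.01 = 0.19.

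| c | Ketamine-arm use | With infusion (b = 3; 5) | Without infusion (b = 3; 5) | Contrast (b = 3; 5) |
|---|---|---|---|---|
| 0 | 50% | 0; 0 | 0; 0 | 0; 0 |
| 0.25 | 40% | 0.35; 0.58 | 0.32; 0.53 | 0.03; 0.05 |
| 0.5 | 31% | 0.72; 1.20 | 0.61; 1.01 | 0.11; 0.19 |
| 1.0 | 16% | 1.53; 2.55 | 1.07; 1.79 | 0.46; 0.76 |

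Positive values mean that ketamine's benefit is understated.

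**Cross-check.** A separate simulation (4 million subjects, true difference −8.1, SD 8.9) set the correlation between the latent factor and MADRS change at 0, 0.3 or 0.5. Falls in exposure of 10 to 30 percentage points gave within-subgroup bias of about 0.3 to 1.9 points when that correlation was 0.3 or 0.5. Bias was about 0 (0.02 or less) when exposure did not shift or when the correlation was 0. The overall effect stayed at −8.1 throughout.

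**Precision.** With an assumed even split (10 per arm per subgroup) and SD 8.9, the standard error of the contrast between two subgroup effects is √(4 × 8.9²/10) = 5.6 points.

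**The case against.** The strongest reply is that the documents show neither condition that bias requires: that ketamine shifts the exposure, and that the exposure shares causes with MADRS. This stands. A reader might infer from 27c that these subgroup effects are biased; the documents support only that they may be.

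A reader might also infer that all three exposures arise during or after the study infusion. That is not documented. Nitrous oxide or an opioid infusion could be started at induction, and a catheter placed before surgery and merely used afterwards. Their listing in 25c beside type of surgery and type of anesthesia is consistent with features of technique, though it does not settle timing.

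The opioid outcomes in 26c cover inpatient use and use at Days 7 and 14, not the choice of an intraoperative infusion, and say nothing about nitrous oxide or catheters. So the case is strongest for item 4 and weaker for items 3 and 5, for which no size is estimated.

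In the model above both subgroups are understated in the same direction, so most of the bias cancels in the contrast, and what remains is small beside a standard error of 5.6. The model gives no support for a spurious gain. The analyses are optional, exploratory and unpowered.

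Masking answers less than it seems to. It removes knowledge of the arm, not a clinician's response to the drug's effects. And the silence on timing is itself a reason to define these variables.

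**Conclusion.** The point holds as a possible bias in exploratory analyses that a change of wording would remove. Three of the five examples use exposures observed after randomization, with no safeguard in 27c.

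For opioid infusions, bias within a subgroup ranges from 0 to about 2.6 MADRS points and bias in the between-subgroup contrast from 0 to about 0.8, against a planning difference of 8.1. These ranges rest wholly on the assumed prevalence, the 0.7 correlation, the 3 to 5 point loading and a shift of 0 to 1 SD. Zero is a legitimate end of the range.

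The primary MADRS analysis and the main secondary outcomes do not use these splits and are unaffected.

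**What to change.** In SAP 27c:
- Keep items 1 and 2 as subgroup analyses.
- Define items 3 to 5 by the anesthetic or analgesic plan, or the catheter status, recorded before the study infusion starts.
- Where no such record exists, tabulate the exposure by arm. Label any split by it as descriptive, not as evidence of who benefits or of mechanism.

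Section 25c already collects these variables, so the table needs little more than a breakdown by arm. The change alters no patient care, no sample size and no primary analysis. The downside is that one or more exploratory subgroup comparisons may be lost or reduced to description.
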